8.6 Discontinuation from follow-up

If a patient withdraws from further follow-up the appropriate eCRF form should be submitted to ICR-CTSU stating whether the patient has withdrawn consent for information to be sent to the ICR-CTSU or whether they simply no longer wish to attend trial follow up visits. In the very rare event that a patient requests that their data is removed from the study entirely, the implications of this should be discussed with the patient first to ensure that this is their intent and, if confirmed, ICR-CTSU should be notified in writing.

8.7 Radiological evaluation of SBRT treated metastatic lesions

It is acknowledged that response assessment of lesions to SBRT may be difficult particularly at early imaging time points. This is particularly relevant in the interpretation of response with liver metastases. Caution must be used in interpretation as post-treatment changes may mimic tumour progression. Therefore if there is suspicion of local progression on follow up CT scans, consideration should be given to performing additional imaging in the form of MRI and/or PET/CT for diagnostic clarification. If no conclusion can be drawn, a second CT, MRI or PET/CT at least 8 weeks apart should be performed to confirm disease progression.

8.8 Schedule of assessments

| Visit/Assessments/ Procedures | Pre-randomisation | Pre-treatment | End of trial treatment for SBRT + SOC group or equivalent for SOC group | Time from randomisation | | | | | | | | | | | | | |
|--|-------------------|---------------------------------------|---|-------------------------|-----|------------------|------|------------------|------------------|------------------|------|------------------|------------------|----------------|------------------|----------------|------------------|
| | Within 42 days | Following confirmation of eligibility | SBRT + SOC group: within +/- 7days of last SBRT treatment SOC only group: within 6 weeks after randomisation | 3 M | 6 M | 9 M | 12 M | 15 M | 18 M | 21 M | 24 M | 30 M | 36 M | 42 M | 48 M | 54 M | 60 M |
| Informed consent | X | | | | | | | | | | | | | | | | |
| Histological confirmation of primary breast, prostate or NSCLC | X* | | | | | | | | | | | | | | | | |
| Complete medical history | X | | | | | | | | | | | | | | | | |
| Physical examination including WHO performance status, body weight, height, blood pressure (BP at baseline only) | X | | X | X | X | X | X | X | X | X | X | X | X | X | X | X | X |
| Tumour primary assessment using RECIST v.1.1 criteria | X | | | X ^{B,L} | X | X ^{B,L} | X | X ^{B,L} | X ^{B,L} | X ^{B,L} | X | X ^{B,L} | X ^{B,L} | X ^B | X ^{B,L} | X ^B | X ^{B,L} |
| Concomitant therapy assessment | | X | X | | | | | | | | | | | | | | |
| Full blood count, urea and electrolytes, LFTs | | X | | | X | | | | | | | | | | | | |
| Pregnancy test (for women of childbearing potential) | X | | | | | | | | | | | | | | | | |
| Symptom assessment using NCI | | X | X | X | X | X | X | X | X | X | X | X | X | X | X | X | X |

| Visit/Assessments/ Procedures | Pre-randomisation | Pre-treatment | End of trial treatment for SBRT + SOC group or equivalent for SOC group | Time from randomisation | | | | | | | | | | | | | |
|---|-------------------|---------------------------------------|---|-------------------------|----------------|----------------|----------------|----------------|----------------|----------------|----------------|----------------|----------------|----------------|----------------|----------------|----------------|
| | Within 42 days | Following confirmation of eligibility | SBRT + SOC group: within +/- 7days of last SBRT treatment SOC only group: within 6 weeks after randomisation | 3 M | 6 M | 9 M | 12 M | 15 M | 18 M | 21 M | 24 M | 30 M | 36 M | 42 M | 48 M | 54 M | 60 M |
| CTCAE v.4.0 | | | | | | | | | | | | | | | | | |
| Symptom assessment using RTOG | | X | | | X | X | X | X | X | X | X | X | X | X | X | X | X |
| Quality of life questionnaire (EORTC QLQ C30 and EQ-5D) | | X** | X | X | X | | X | | X | | X | | | | | | |
| Placement of fiducial markers (optional) | | X | | | | | | | | | | | | | | | |
| NSCLC primary patients only: CT scan of chest, abdomen and pelvis | X ² | | | X ² | X ² | X ² | X ² | X ² | X ² | X ² | X ² | X ² | X ² | | X ² | | X ² |
| NSCLC primary patients only: CT brain with contrast or MRI brain with contrast | X | | | | | | | | | | | | | | | | |
| Breast primary patients only: Ca 15-3 (optional) | X | | | X | X | X | X | X | X | X | X | X | X | X | X | X | X |
| Breast primary patients only: CT scan of chest, abdomen and pelvis | X ² | | | X ² | X ² | X ² | X ² | X ² | X ² | X ² | X ² | X ² | X ² | X ² | X ² | X ² | X ² |
| Prostate primary patients only: PSA | X ¹ | | | X ¹ | X | X ¹ | X | X ¹ | X ¹ | X ¹ | X | X ¹ | X ¹ | X ¹ | X ¹ | X ¹ | X ¹ |
| Prostate primary patients only: Testosterone | X | | | | | | X | | | | X | | X | | X | | X |

| Visit/Assessments/ Procedures | Pre-randomisation | Pre-treatment | End of trial treatment for SBRT + SOC group or equivalent for SOC group | Time from randomisation | | | | | | | | | | | | | |
|---|-------------------|---------------------------------------|---|-------------------------|----------------|-----|----------------|------|------|------|------|----------------|------|------|------|------|------|
| | Within 42 days | Following confirmation of eligibility | SBRT + SOC group: within +/- 7days of last SBRT treatment SOC only group: within 6 weeks after randomisation | 3 M | 6 M | 9 M | 12 M | 15 M | 18 M | 21 M | 24 M | 30 M | 36 M | 42 M | 48 M | 54 M | 60 M |
| Prostate primary patients only: Bone and CT scan of chest, abdomen and pelvis | X ³ | | | | X ³ | | X ³ | | | | | X ³ | | | | | |
| Liver metastases only: Clotting screen (INR), LFTs and optional DMSA scan or equivalent as per local guidelines | X | | | | | | | | | | | | | | | | |
| Liver metastases only : Clotting screen (INR) and LFTs (ALT/AST, bilirubin and albumin) | | X | | X | X | | X | | | | | | | | | | |
| Spinal metastases only: MRI whole spine | X | | | | | | | | | | | | | | | | |
| Lung metastases only: Pulmonary function tests (FEV 1, FVC, and TLCO/KCO) (at baseline only and then as per symptoms) ^L | X | | | | | | | | | | | | | | | | |

Footnotes:

M = month

X^{*} = will be before 42 days prior to randomisation

X** = within one week prior to randomisation or if this window is missed should be before treatment allocation is known to the patient (SOC or SBRT + SOC).

1. PSA levels may indicate the need for an unscheduled bone and CT scan. This may be replaced by choline or PSMA PET/CT scan or wb-dwMRI if locally available. Where scanning has been indicated tumour assessment according to RECIST v1.1 criteria should be carried out, where possible.

2. *NSCLC and breast patients*: CT scans of chest, abdomen and pelvis. Scans may be replaced by FDG PET-CT scan as long as the CT scan is of diagnostic quality, or whole body dwMRI if locally available.

3. Prostate patients: Bone and CT scans of chest, abdomen and pelvis. These may be replaced by choline or PSMA-PET or wb-dwMRI if locally available

B = breast

L= NSCLC

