| 
FOLLOW UP
 | 
All patients will be reviewed every 3 months with a clinical examination and tumour markers (where applicable) during years 1 and 2, and 6 monthly thereafter up to 5 years. Staging and follow up imaging protocols will be tumour type dependent:
 
 • Breast = 3 monthly CT scans for years 1 & 2, and 6 monthly thereafter to 5 years. • NSCLC = 3 monthly CT scans for years 1 & 2, 6 monthly to year 3 and then annually to year 5. • Prostate = CT will be performed at 6, 12 and 24 months with imaging triggered by appropriate PSA rises. A rising PSA defined as 2 successive PSA rises from nadir, measured a minimum of 4 weeks apart. If the overall PSA rise has a doubling time of ≥ 3 months or |

| | |
|--|---|
| | 
the PSA level has doubled the original PSA value at trial entry or if clinically indicated, then restaging should be considered.
 
All patients will have a toxicity assessment at each clinic visit and patient reported quality of life (QOL) assessment at 3, 6, 12, 18 & 24 months.
 |
|--|---|

TRIAL SCHEMA

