3 TRIAL DESIGN

CORE is a phase II/III, multi-centre, non-blinded, parallel group randomised controlled trial in patients with breast, prostate or NSCLC primary cancer comparing standard of care (SOC) with or without SBRT for extra-cranial metastases. The aim of the phase II study is to demonstrate 1) feasibility of recruitment, 2) deliverability of the study in a multi-centre setting and 3) activity of SBRT, based on progression free survival, across the three tumour types. If all three aims are achieved the trial will be amended to roll into parallel tumour-site specific phase III trials.

Eligible patients are those with either primary breast, prostate or NSCLC who have presented with ≤ 3 extra-cranial, metachronous, oligometastases, all suitable for SBRT. Patients will be randomised in a 1:1 ratio to either SOC or SOC with the addition of SBRT. Choice of SOC treatment is at the discretion of the local oncologist and defined per patient prior to randomisation (see Section 9 Trial Treatment). Patients randomised to SBRT+SOC will receive a dose and fractionation regimen dependent on the metastatic site and proximity to dose limiting organs and normal tissues. Treatment will take place within 6 weeks of randomisation. The average scheme would be 3 treatments over 5 days but the maximum period of SBRT duration could be 8 treatments over 19 days.

All patients will be reviewed every 3 months with a clinical examination and tumour markers (where applicable) during years 1 and 2, and 6 monthly thereafter to 5 years. Staging and follow up imaging protocols will be tumour type dependent:

- **Breast:** 3 monthly CT scans for years 1 and 2, and 6 monthly thereafter to 5 years.
- **NSCLC:** 3 monthly CT scans for years 1 and 2, 6 monthly to year 3, then annually to 5 years.
- **Prostate:** CT scans will be performed at 6, 12 and 24 months with imaging triggered by appropriate PSA rises. A rising PSA defined as 2 successive PSA rises from nadir, measured a minimum of 4 weeks apart, will be used to trigger additional imaging (CT) between these time points.

All patients will have a toxicity assessment at each clinic visit and patient reported quality of life (QOL) assessment at 3, 6, 12, 18 and 24 months.

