8.3.4 Prostate Primary patients

The following assessments should be conducted for all prostate primary patients at each follow up visit (Months 3, 6, 9, 12, 15, 18, 21, 24, 30, 36, 42, 48, 54 and 60 months post randomisation):

- Physical examination including WHO performance status, weight and height.
- Assessment of late toxicity using NCI CTCAE v.4.0 and RTOG (RTOG is excluded for 3 month post randomisation).
- Assessment of tumour marker PSA.

A rise in PSA levels may indicate the need for unscheduled bone and CT scan. Scans may be replaced by choline or PSMA PET/CT scan or whole body dwMRI if locally available. A rising PSA is defined as 2 successive PSA rises from nadir, measured a minimum of 4 weeks apart. If the overall PSA rise has a doubling time of ≥ 3 months or the PSA level has doubled the original PSA value at trial entry or if clinically indicated, then restaging should be considered. Where scanning has been indicated tumour assessment according to RECIST v1.1 criteria should be carried out, where possible.

In addition the following assessments should be performed:

6, 12 and 24 months after randomisation

- Bone and CT scan of chest, abdomen and pelvis. These may be replaced by choline or PSMA PET/CT or wb-dwMRI if locally available.
- Tumour assessment according to RECIST v.1.1 criteria, where possible. In instances where RECIST assessment is not possible assessment by other methods should be considered or a clinical assessment of widespread progression should be performed.

Month 6 post randomisation

- Full blood count, urea, electrolytes and LFTs (ALT/AST, bilirubin, albumin).

Months 3, 6, 12, 18 and 24 post randomisation

- Quality of life questionnaire (EORTC QLQ C30 and EQ5D)

Months 12, 24, 36, 48 and 60 post randomisation

- Assessment of testosterone

8.3.5 Liver metastases:

In addition to the assessments outlined for the primary tumour patients the following assessments should be performed for patients with liver metastases as indicated:

| | |
|-------------------------------|---|
| 3 months after randomisation | Clotting screen (INR) and liver function (ALT/AST, bilirubin, and albumin) to ascertain liver function status regarding radiation induced liver disease |
| 6 months after randomisation: | Clotting screen (INR). |
| 12 months after randomisation | Clotting screen (INR), liver function (ALT/AST, bilirubin and albumin) to ascertain liver function status regarding radiation induced liver disease |

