11.1.2 Sample size

This phase II screening study has been designed with a primary endpoint of PFS, and relaxed one-sided $\alpha=0.20$ and $\beta=0.20$ (13). The control arm PFS is estimated based on the expected contribution of each primary tumour site to the overall final sample size. Based on observed recruitment in the first year this is estimated at 75% prostate, 14% breast and 11% lung. Assuming a median PFS of 5 months for NSCLC, 12 months for breast and 18 months for prostate patients (14-22), it is estimated that the median PFS in the control group after randomisation will be 16 months. The phase II SABR-COMET trial targets a hazard ratio (HR) for OS of 0.6 (23). For CORE, a more conservative effect size has been chosen reflecting clinical opinion of what would constitute a PFS signal worthy of a phase III OS trial. In order to detect a HR of 0.75 for improvement of PFS i.e. extending the median cohort PFS by 4 months in the experimental arm with 80% power, a total of 230 patients are required (138 events). Assuming a 5% rate of patients lost to follow up at the point of data analysis, a total of 242 patients will be required (121 per treatment group). Dependent on observed rates of accrual this total may increase to a maximum of 270 to allow for each cohort to achieve a minimum of 50 patients. The sample size calculations, made using the *artsurv* command in Stata version 13, assume 50% recruited in both years 1 and 2 and 12 months of additional follow up.

The decision rule to proceed to phase III will be based on a 3 outcome design. An overall result significant at the 10% level would support continuation to phase III; significance between 10% and 20% would require supportive evidence from secondary endpoints with a particular emphasis on local tumour control and FFWMD. If the significance is >20% then the study will not progress to phase III unless there is clear

heterogeneity of outcomes between the 3 tumour subgroups supporting a signal in selected tumour sites in which case consideration would be given to progressing to an extended phase 2 evaluation for that tumour site alone.

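### The schedule table puts the last scheduled prostate bone/CT scan at 30 months, while the text and the table's RECIST row point to 24 months; the passages must be reconciled

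*Protocol*

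**What the plan says.** Three places in the Protocol give the same prostate imaging months. Section 3 says "CT scans will be performed at 6, 12 and 24 months with imaging triggered by appropriate PSA rises", the trial summary says the same in almost identical words, and section 8.3.4 lists the bone and CT scans under "6, 12 and 24 months after randomisation".

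The schedule table in 8.8 has a separate row for these scans, "Prostate primary patients only: Bone and CT scan of chest, abdomen and pelvis". As extracted, its marks fall at pre-randomisation, 6, 12 and 30 months, and the 24-month cell is empty.

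Two other rows of that table bear on the point:

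- The row "Tumour primary assessment using RECIST v.1.1 criteria" has an unrestricted mark at 6, 12 and 24 months. Its 30-month mark is restricted to breast and NSCLC.
- The row "Prostate primary patients only: PSA" carries the footnote about a possible unscheduled scan at every visit except 6, 12 and 24 months. At 30 months the footnote is present.

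Section 3 adds that a rising PSA "will be used to trigger additional imaging (CT) between these time points". On case mix, 11.1.2 states: "Based on observed recruitment in the first year this is estimated at 75% prostate, 14% breast and 11% lung".

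**The concern.** Read literally, the table asks for a prostate RECIST assessment at 24 months with no scan to base it on, and for a scan at 30 months with no RECIST assessment attached. The schedule table is what many sites book from, so some may follow it and others the text.

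What is at stake is the dating of radiological progression in prostate patients: PFS events without a PSA rise, local lesion control, and freedom from widespread metastatic disease (FFWMD). The last two are defined by radiological evidence (11.2.2, 11.2.3), which PSA cannot supply. Under 11.1.2 they are also the secondary endpoints given most weight in the phase III decision when the primary result lies between the 10% and 20% levels.

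**Working it through.** **Is the mark really in the 30-month column?** The table header has a label plus 17 columns: pre-randomisation, pre-treatment, end of treatment, and 14 visits from 3 to 60 months. The prostate scan row also has a label plus 17 cells. Counting across, four empty cells (15, 18, 21 and 24 months) lie between the 12-month mark and the last mark, which therefore falls at 30 months. Counted the same way, the testosterone, quality-of-life and NSCLC CT rows agree with the months in their text.

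**The passages side by side**

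| Place | Prostate months after randomisation |
|---|---|
| Trial summary; section 3; section 8.3.4 | 6, 12, 24 |
| 8.8, RECIST row (marks that include prostate) | 6, 12, 24 |
| 8.8, PSA row (unscheduled-scan footnote absent) | 6, 12, 24 |
| 8.8, prostate bone/CT row | 6, 12, 30 |

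**Interval after month 12.** Text: 24 − 12 = 12 months. Scan row: 30 − 12 = 18 months. The difference is 6 months.

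**Patients to whom a third post-randomisation scan would apply by the analysis**

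Inputs from 11.1.2: 75% prostate; 230 patients; prostate control median PFS 18 months; half the patients recruited in each of two years, then 12 months of follow-up. Assumptions added here: accrual uniform within the 24 months, exponential PFS, and the control median applied to both arms.

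- Prostate patients: 0.75 × 230 = 172.5, taken as 172.
- Potential follow-up is uniform on 12 to 36 months. Share reaching 24 months: (36 − 24)/24 = 0.50. Share reaching 30 months: (36 − 30)/24 = 0.25.
- Progression-free: S(24) = 2^(−24/18) = 0.397; S(30) = 2^(−30/18) = 0.315.
- Progression-free and due a 24-month scan: 172 × 0.50 × 0.397 ≈ 34.
- Progression-free and due a 30-month scan: 172 × 0.25 × 0.315 ≈ 14.

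**Sensitivity**

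- 242 patients: 0.75 × 242 = 181.5, giving about 36 and 14.
- 270 patients with at least 50 in each cohort: prostate at most 270 − 100 = 170 (63%), giving about 34 and 13.
- Target hazard ratio of 0.75 in the SBRT arm: S(24) = 2^(−1) = 0.50 and S(30) = 2^(−1.25) = 0.42 in that arm. Averaging the arms gives 86 × (0.397 + 0.50)/2 ≈ 39 and 43 × (0.315 + 0.42)/2 ≈ 16, where 86 = 172 × 0.50 and 43 = 172 × 0.25.

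**The case against.** **It may be a reading error.** The prostate scan row opens a new page block of the table. In that block the only other row with post-randomisation marks is the liver function row, at 3, 6 and 12 months, so nothing there tests alignment to the right of 12 months. A single mark shifted by one column in a sparse row would look the same. This stands as a reason to check the original page. The full cell count argues against a shift but does not exclude it.

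**A reader might infer that the protocol as such leaves an 18-month scan gap in three quarters of the trial.** It does not. The gap arises only at a site that follows this row over the dedicated prostate section, the design section and the summary. The RECIST assessment due at 24 months already signals that imaging is expected then.

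**A reader might also infer that PFS goes unobserved in the gap.** PSA is measured every 3 months to month 24 and 6-monthly afterwards, and rises can prompt imaging. PSA progression is considered for prostate PFS (11.2.1), and event-free prostate patients are censored at their last PSA assessment (11.2.4). The cover is partial, because under 8.3.4 a PSA rise leads to consideration of restaging and not to a mandatory scan. After progression, 8.4 allows imaging by local practice, so FFWMD does not rest on the scheduled scans alone.

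**Larger counts are tempting.** Calendar follow-up alone gives 172 × 0.50 = 86 against 172 × 0.25 = 43, but those figures include patients who have already progressed and left protocol-timed imaging. Similarly, 2^(−12/18) − 2^(−30/18) = 0.630 − 0.315 = 0.315, or about 54 of 172, is the number progressing between months 12 and 30. It is not a count of missed or misdated events.

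**Bias between arms is not shown.** Centre is a minimisation factor (11.1.3), so differences in scan timing between sites should fall about equally on both groups.

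**Conclusion.** The inconsistency is real on the text as extracted and should be corrected. One operative row of 8.8 disagrees with three passages of text and with two other rows of its own table. Where a site follows that row, the third scheduled post-randomisation scan comes 6 months later.

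On the stated accrual, exponential 18-month PFS for all and 172 prostate patients, about 34 would be progression-free and due that scan by the analysis under the text, against about 14 under the row. The sensitivity cases give 34 to 39 against 13 to 16. These counts are before any PSA-triggered imaging and suppose that every site follows the same passage, so they bound the effect and do not estimate it.

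The expected harm is later and site-dependent dating of radiological progression. The 6- and 12-month scans agree everywhere, so the 1-year time point of interest is unaffected. The log-rank and Cox analyses use the whole of follow-up and could be touched slightly. No sample-size figure depends on this point.

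**What to change.** Check the original page of 8.8 to confirm where the mark falls. If it is as extracted, reconcile the prostate bone/CT row with section 3, section 8.3.4, the trial summary and the table's own RECIST and PSA rows, so that all give one set of scan months. Which months are intended is for the sponsor to state. Then notify sites, so that those booking from the table and those booking from the text work to the same dates.

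The cost is a correction to the table and a notice to sites. The number of scheduled scans does not change, since the row and the text each list three after randomisation.

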9 TRIAL TREATMENT

9.1 SBRT treatment

Patients randomised to receive SBRT+SOC will receive an SBRT dose and fractionation regimen dependent on the metastatic site and proximity to normal tissues.

9.1.1 Treatment timelines

To allow sufficient time for treatment planning, SBRT can commence up to 6 weeks after randomisation.

9.1.2 Radiotherapy planning

Radiotherapy planning and outlining should be carried out in accordance with the guidelines in the current version of the Radiotherapy Planning and Delivery Guidelines document, available on request from ICR-CTSU ([contact]) or via the Radiotherapy website (www.rtrialsqa.org.uk). Fiducial marker insertion, where necessary, should be conducted according to local guidelines, ensuring SBRT treatment can commence within the 6 week timeframe from randomisation.

9.1.3 Treatment technique

Highly conformal treatment planning is a pre-requisite for SBRT. SBRT may be delivered using a specialist SBRT platform, such as CyberKnife, or with a linear accelerator with SBRT capabilities. Any SBRT delivery platform is acceptable as long as the individual centre has demonstrated they are able to comply with the radiotherapy standards laid out in this protocol and the Radiotherapy Planning and Delivery Guidelines document.

